Appendix K General guidance for the follow-up of laboratory abnormalities by Sanofi

NEUTROPENIA

[figure not shown]

Note:

- The procedures described in the above flowchart are to be discussed with the patient only in case the event occurs. If applicable (according to local regulations), an additional consent (e.g., for HIV testing) will only be obtained in the case the event actually occurs.
- For individuals of African descent, the relevant value of concern is <1000/mm³

Neutropenia is to be recorded as an AE only if at least 1 of the criteria listed in the general guidelines for reporting AEs in [Section 10.4.3](#) is met.

[figure not shown]
THROMBOCYTOPENIA

Note:

The procedures above flowchart are to be discussed with the patient only in case described in the the event occurs. If applicable (according to local regulations), an additional consent (e.g., for HIV testing) will only be obtained in the case the event actually occurs.

Thrombocytopenia is to be recorded as an AE only if at least 1 of the criteria listed in the general guidelines for reporting AEs in [Section 10.4.3](#) is met.

[figure not shown]

- *If unable to retest in 72 hours, use original lab results to decide on further reporting/monitoring/discontinuation.
- Note:
- “Baseline” refers to ALT sampled at baseline visit; or if baseline value unavailable, to the latest ALT sampled before the baseline visit. The algorithm does not apply to the instances of increase in ALT during screening.

See [Section 10.4](#) for guidance on safety reporting.

[figure not shown]
- Normalization is defined as \leq ULN or baseline value, if baseline value is $>$ ULN.

ACUTE RENAL FAILURE

Acute renal failure is to be recorded as an AE only if at least 1 of the criteria listed in the general guidelines for reporting AEs in [Section 10.4.3](#) is met.

SUSPICION OF RHABDOMYOLYSIS

Suspicion of rhabdomyolysis is to be recorded as an AE only if at least 1 of the criteria in the general guidelines for reporting AEs in [Section 10.4.3](#) is met.

Appendix L Clinically significant ECG

The following list of ECG findings is considered to be clinically significant and would result in the exclusion of the patient from the study based upon Exclusion criterion 15 [[E 15](#)]. This list is not exhaustive in nature but serves as a guide to help determine clinical significance with regards to ECG for the safety of the patient who is being considered for this study.

If there is a question pertaining to another clinically significant finding not described below, it must be brought to the attention of Sanofi before consideration of enrollment. Sanofi will then provide timely recommendation after internal review regarding the patient's eligibility associated with this exclusion criterion.

Clinically significant ECG finding that would meet Exclusion criterion 15 [[E 15](#)]:

- Second-degree heart block
- Third-degree heart block
- QT prolongation (*symptomatic*)
- Sick sinus syndrome
- Left bundle branch block (*complete*)
- Right bundle branch block (*complete*)
- Atrial fibrillation (*uncontrolled*)
- Atrial flutter (*uncontrolled*)
- Wolff-Parkinson-White syndrome
- Atrioventricular nodal reentry tachycardia
- Ventricular Arrhythmias
 - Ventricular Tachycardia
 - Ventricular Fibrillation
 - Torsades de Pointes
 - Bradyarrhythmias

ACT14604 Amended Protocol01

ELECTRONIC SIGNATURES

Signed by	Meaning of Signature	Server Date (dd-MMM-yyyy HH:mm)
[REDACTED]	Clinical Approval	09-Aug-2017 13:53 GMT+0200
[REDACTED]	Clinical Approval	09-Aug-2017 16:48 GMT+0200

ATC:	anatomic or therapeutic categories
AUC:	area under the curve
BM:	biomarker
BMI:	body mass index
CCL2:	chemokine (C-C motif) ligand 2
CMQ:	customized MedDRA query
COMP:	cartilage oligomeric matrix Protein
cpk:	creatinine phosphokinase
CRISS:	composite response index for diffuse cutaneous systemic sclerosis
dcSSc:	diffuse cutaneous systemic sclerosis
EBLUP:	empirical best linear unbiased prediction
ECL:	electrochemiluminescence
e-CRF:	electronic case report form
ELISA:	enzyme linked immuno sorbent assay
ESR:	erythrocyte sedimentation rate
FVC:	forced vital capacity
HEVA:	health economics and value assessment
HLGT:	high-level group term
HLT:	high-level term
HRCT:	high resolution computer tomography
hsCRP:	high-sensitivity C-reactive protein
ILD:	interstitial lung disease
IMP:	investigational medicinal product
IRT:	interactive response technology
ITT:	intent-to-treat
LLT:	lower level term
MAR:	missing at random
MedDRA:	Medical Dictionary for Regulatory Activities
MMRM:	mixed model with repeated measures
mRSS:	modified Rodnan skin score
NMAR:	not missing at random
PAH:	pulmonary arterial hypertension
PK:	pharmacokinetics
PT:	preferred term

QOL:	quality of life
QQ:	quantile
SAE:	serious adverse event
SD:	standard deviation
SHAQ:	scleroderma health assessment questionnaire
SMQ:	standardized MedDRA query
SOC:	systemic organ class
SSc:	systemic sclerosis
TBILI:	total bilirubine
TJC28:	tender joint count 28
UCLA SCTC GIT 2.0:	UCLA scleroderma clinical trial consortium gastrointestinal tract 2.0
WHO-DD:	World Health Organization Drug Dictionary

1 OVERVIEW AND INVESTIGATIONAL PLAN

1.1 STUDY DESIGN AND RANDOMIZATION

This study will be a multinational, randomized, double blind, placebo controlled, 2 parallel groups, proof of concept Phase 2 study to assess the efficacy and safety of SAR156597 200 mg administered subcutaneously once a week over a 24 week period to patients with diffuse Systemic Sclerosis (SSc).

After a screening phase of up to 4 weeks, patients will be centrally randomized (using allocation from block randomization schedule with stratifying factors) via Interactive Response Technology (IRT) in a 1:1 ratio to 1 of the 2 treatment groups and treated double-blind for approximately 6 months.

Randomization will be stratified based upon the patients' medical history of SSc ILD (yes or no).

1.2 OBJECTIVES

1.2.1 Primary objectives

To evaluate, in comparison with placebo, the efficacy of SAR156597 administered subcutaneously for 24 weeks on skin fibrosis in patients with diffuse cutaneous SSc (dcSSc).

1.2.2 Secondary objectives

The secondary objectives are:

- To evaluate the efficacy of SAR156597 compared to placebo on physical/functional disability in patients with dcSSc.
- To evaluate the efficacy of SAR156597 compared to placebo on respiratory function of patients with dcSSc.
- To evaluate the safety profile of SAR156597 compared to placebo in patients with dcSSc.
- To evaluate the potential for immunogenicity (Anti-drug antibodies (ADA) response) of SAR156597 in patients with dcSSc.
- To evaluate the Pharmacokinetics (PK) (trough plasma concentrations) of SAR156597 administered subcutaneously for 24 weeks.

1.2.3 Exploratory objectives

The exploratory objectives are:

- To explore the efficacy of SAR156597 compared to placebo on other manifestations of SSc (gastrointestinal, joint pain, cardiovascular and renal manifestations) in patients with dcSSc.
- To explore the effect of SAR156597 on the Quality Of Life in patients with dcSSc.
- To measure the effect of SAR156597 on biomarkers of the disease activity and the IL 4/IL 13 pathway.
- To identify biomarkers predictive of response to treatment as defined by mRSS endpoints.

1.3 DETERMINATION OF SAMPLE SIZE

The targeted treatment benefit is a difference of 4 points between treatment groups in the mean change in mRSS from baseline to Week 24.

The impact of treatment discontinuations in the context of an ITT analysis where all modified Rodnan Skin Score (mRSS) data will be included in the analysis (regardless of adherence to treatment) was evaluated. Assuming that 10% of patients will discontinue the treatment, the estimated treatment effect at 24 weeks will be decreased from 4 (targeted treatment effect if all patients adhered to treatment) to 3.6 (targeted treatment effect in all randomized patients).

Ninety four (94) patients (47 patients each in SAR156597 and placebo groups) will yield 80% power to detect a difference between SAR156597 and placebo groups of 3.6 in the mean change from baseline in mRSS at 24 weeks, assuming a Standard Deviation (SD) of 7 and using a 1 sided alpha of 5% (Type I error).

Table 1 provides power calculations depending on several assumptions for treatment effect (difference between treatment groups in the mean change in mRSS from baseline to Week 24) and SD of the response (1) (assumed to be the same in both groups (2, 3).

Table 1 - Power calculations for mRSS, depending on treatment effect and standard deviation, using a 1-sided alpha of 0.05

Treatment effect	SD	Power
$\Delta=3$	8	57%
	7	67%
	6	78%
$\Delta=3.6$	8	70%
	7	80%
	6	90%
$\Delta=4$	8	78%
	7	87%
	6	94%

Calculations were made using East 6.3 software.

1.4 STUDY PLAN

[figure not shown]
Approximately 94 patients will be randomized in a ratio 1:1 to the following two treatment groups:

- SAR156597 group (n=47): Patients will receive SAR156597 administered subcutaneously in 200 mg doses qw.
- Placebo group (n=47): Patients will receive placebo subcutaneously qw.

Randomization will be stratified based upon the patients' medical history of SSc-ILD (yes or no).

The following figure presents the graphical study design.

Figure 1 - Graphical study design (screening period, double-blind period and follow-up period)

1.5 MODIFICATIONS TO THE STATISTICAL SECTION OF THE PROTOCOL

The statistical section of the protocol was never changed in an amendment.

1.6 STATISTICAL MODIFICATIONS MADE IN THE STATISTICAL ANALYSIS PLAN

Some minor modifications were done in this new version:

- A second definition of background therapy was added ([Section 2.4.2](#)).
- The description of all efficacy endpoints at each visit was added ([Section 2.4.4](#)).
- One sensitivity analysis on high mRSS was added ([Section 2.4.4.1.6](#)).

- Three subgroups were added to analyze the primary criteria: second definition of background therapy, geographical region and ANA staining pattern ([Section 2.4.4.1.8](#)).
- The [Section 2.4.4.4.8](#) and [Section 2.4.4.4.9](#) were updated according to the [Appendix B](#) from SAP.
- The observed FVC at Week 24 will be analyzed instead of the change in observed FVC from baseline to Week 24 in the linear mixed model ([Section 2.4.4.4.2](#)).

2 STATISTICAL AND ANALYTICAL PROCEDURES

2.1 ANALYSIS ENDPOINTS

2.1.1 Demographic and baseline characteristics

The baseline value is defined as the last available value before the first administration of the Investigation Medicinal Product (IMP).

All baseline safety and efficacy parameters are presented along with the on-treatment summary statistics in the safety and efficacy sections ([Section 2.4.4](#) and [Section 2.4.5](#)).

Demographic characteristics

Demographic variables are gender (Male, Female), ethnicity (Hispanic or Latino, Not Hispanic or Latino, Not reported, Unknown), race (American Indian or Alaska Native, Asian, Black or African American, Native Hawaiian or other Pacific Islander, White, Not reported, Unknown), age in years (quantitative and qualitative variable: <45, [45-65[, [65-75[and ≥ 75 years) and Body Mass Index (BMI) in kg/m² (quantitative variable and qualitative variable: <30 and ≥ 30).

Medical or surgical history

Medical (or surgical) history includes previous relevant medical and surgery history collected at baseline.

This information will be coded using the version of Medical Dictionary for Regulatory Activities (MedDRA) currently in effect at Sanofi at the time of database lock.

Disease characteristics at baseline

Specific disease history includes disease duration from the time of first non-Raynaud's phenomenon manifestation (months), any systemic sclerosis history and mRSS at baseline. The auto-antibodies specific to systemic sclerosis (centromere antibodies, RNA polymerase III antibody, Scl-70 antibody and ANA staining pattern) and stratification factor (with/without medical history of SSc-ILD) as per IRT and as per electronic case report form (e-CRF) will be also presented.

Alcohol habits at baseline

Alcohol habits (frequency of alcoholic drinks in the last 12 months (Never/At least monthly/At least weekly/At least daily/Occasionally), number of standard drinks (1 or 2/Greater than 2 where standard drink means 1 pint/bottle of beer, 1 glass of wine, 1 shot of hard liquor...) per day when drinking alcohol.

Other baseline characteristics

Other baseline characteristics include weight in kilograms (quantitative variable and qualitative variable: <50, [50-100[, ≥100).

Any technical details related to computation, dates, and imputations for missing dates are described in [Section 2.5](#).

2.1.2 Prior or concomitant medications

All immunosuppressive and investigational drugs taken within 3 months before screening visit, all antibiotics taken within 1 month before screening visit, and all medications taken within 28 days prior to baseline visit and until the end of the study are to be reported in the case report form pages.

All medications will be coded using the World Health Organization-Drug Dictionary (WHO-DD) using the version currently in effect at Sanofi at the time of database lock.

- Prior medications are those the patient used prior (from 3 months before screening visit) to first investigational medicinal product (IMP) intake. Prior medications can be discontinued before first administration or can be ongoing during treatment phase.
- Concomitant medications are any treatments received by the patient concomitantly to the IMP, from randomization to the end of treatment + 84 days. A given medication can be classified both as a prior medication and as a concomitant medication. Concomitant medications do not include medications started during the post-treatment period (as defined in the observation period in [Section 2.1.5](#)).
- Post-treatment medications are those the patient took in the period running from the day after last administration of IMP + 84 days up to the end of the study.

Any technical details related to computation, dates, imputation for missing dates are described in [Section 2.5](#).

2.1.3 Efficacy endpoints

All measurements, scheduled or unscheduled, will be assigned to analysis windows defined in [Section 2.5.4](#) in order to provide an assessment of the efficacy parameter at each time point planned to be collected as per protocol. For all post-baseline time points, the value used for the analyses at a given time point (eg, at Week 24) is the valid value obtained within the corresponding analysis window. If multiple valid values of a variable exist within an analysis window, the nearest from the targeted study day will be selected. In case of ties, the best value will be considered. The baseline value is the last available and valid measurement obtained up to the date and time of the first double-blind IMP injection. For patients randomized and not treated, the baseline value is defined as the last available and valid value obtained up to the date and time of randomization. All efficacy endpoints will be analyzed using the ITT population.

2.1.3.1 Primary efficacy endpoint(s)

The primary efficacy endpoint will evaluate the efficacy of SAR156597 on skin thickening (ie, fibrosis) of patients with dcSSc by measuring:

- Change in mRSS from baseline to Week 24.

The mRSS assesses skin thickness in 17 body surface areas (face, chest, abdomen, right and left fingers, hands, forearms, upper arms, thighs, lower legs and feet). Each area is assessed for thickness on a 0 to 3 scale (0 = normal, 1 = mild but definite thickening, 2 = moderate skin thickening and 3 = severe skin thickening). The total mRSS score (the sum of score from all 17 body areas) ranges from 0 (no thickening) to 51 (severe thickening in all 17 areas). If one or more the scores from the 17 body areas is missing, then the mRSS is missing (see [Appendix C](#)). The lower the mRSS is, the better it is for the patient.

2.1.3.2 Secondary efficacy endpoints

Two secondary endpoints will evaluate the efficacy of SAR156597 on other aspects of dcSSc:

- Change in HAQ-DI, assessed with SHAQ, from baseline to Week 24.
- Change in respiratory function as measured by observed Forced Vital Capacity (FVC) and observed DLco (corrected for hemoglobin) from baseline to Week 24.

The HAQ-DI assesses the extent of the patient's functional ability; specifically their usual abilities using their usual equipment over the past week. It contains 8 domains of activity (dressing and grooming, arising, eating, walking, hygiene, reach, grip, and common daily activities) each of which has at least 2 questions, for a total of 20 items (see [Appendix D](#)). For each item, patients report the amount of difficulty experienced performing the activity. There are 4 possible responses for each item ranging from 0 (without any difficulty) to 3 (unable to do).

Each domain is scored separately. A domain score is determined from the highest score of the items in that domain. For example, if there are two items (as in the domain "arising"), and the patient responds with a 1 and 2, respectively, to the two items, the score for the "arising" domain will be a 2. If a question is left blank or is confusing, then the score for that category is determined by the remaining completed question(s).

For each of the eight domains there is an "aids or devices" companion variable(s) that is used to record the type of assistance, if any, a patient uses for his/her usual activities. The relationship between aids and devices and the domains (disability categories) is presented in [Table 2](#). Use of aids or devices, or requirement of help from another person impacts on the scoring of the domains. When there are no aids or devices or help indicated for a domain, the category's score is not modified. When aids or devices or help are indicated by the patient, the score for the domain is raised from a 0 or a 1 to a 2, but if the patient's highest score for that domain is a 2 or 3, the score is kept as it is.

No adjustment is made if the patient indicated only "other" under aids or devices, without any other aid, device or help. The data entered at field "Other specify" will not be used for score adjustment.

Table 2 - Relationship between aids or devices and the domains (disability categories)

Disability Category	Aids or devices
Dressing & Grooming	Devices used for dressing (button hook, zipper pull, long handled shoe horn, etc.)
Arising	Built up or special chair
Eating	Built up or special utensils
Walking	Cane, walker, crutches, wheelchair
Hygiene	Raised toilet seat, bathtub seat, bathtub bar Long handled appliances in bathroom
Reach	Long handled appliances for reach
Grip	Jar opener (for jars previously opened)

The HAQ-DI composite score is calculated as the average of the scores of the domains. The patient must have a score for at least 6 of the 8 domains for the composite score to be calculated.

The HAQ-DI composite score is obtained by dividing the sum of the domains by the number of answered domains. This gives a score between 0 (no impairment in function) and 3 (maximal impairment of function).

If less than 6 domains have been scored then the HAQ-DI composite score is missing.

2.1.4 Exploratory endpoints

- Proportion of patients with improvement in mRSS of at least 20%, 40% and 60% from baseline to Week 24.
- Change in VAS for pain, breathing function, vascular function (Raynaud's phenomenon), gastrointestinal function, digital ulcers, and global assessment from SHAQ from baseline to Week 24 (see [Appendix D](#)).

Each VAS is scored between 0 and 100 measuring (using a ruler) how many mm from 0 the patient has placed their mark on the VAS (ie, where the mark crosses the VAS line). Each VAS is scored independently; no total score is calculated. Missing data is considered missing, and not imputed.

- Change in respiratory function as measured by % predicted FVC and % predicted DLco (corrected for hemoglobin) from baseline to Week 24.
- Change in UCLA Scleroderma Clinical Trial Consortium Gastrointestinal Tract 2.0 (UCLA SCTC GIT 2.0) score from baseline to Week 24.

The UCLA SCTC GIT 2.0 Questionnaire includes 34 items and 7 multi-item scales (reflux, distention/bloating, diarrhea, fecal soilage, constipation, emotional well-being, and social functioning) to assess quality of life (QOL) related to gastrointestinal function in patients with SSc. All scales are scored from 0.00 (better QOL) to 3.00 (worse QOL) except the diarrhea and

constipation (range from 0.00-2.00 and 0.00-2.50, respectively). The UCLA SCTC GIT 2.0 questionnaire provides a total score of GIT severity: it is calculated as the average of all scales (except constipation) and ranges from 0.00 to 2.83 (see [Appendix E](#)). If one item is missing, the UCLA SCTC GIT 2.0 score will be considered missing.

- Change in Tender Joint Count 28 (TJC28) from baseline to Week 24.

The TJC28 is an assessment of the overall joint pain based upon the examination of 28 key joints (see [Appendix H](#)). With the individual missing joint score (the “replaced or fused” joints are not taken into consideration with regards to tenderness) imputed as the mean of the scored joints, the tender joint count calculation after imputation is as follows:

- $TJC28 = \text{sum (scored tender joints)} * (\text{number of joints in the full joint set/number of scored tender joints})$.

The number of joints in the full joint set is defined as (28 - number of replaced or fused joints) and the scored joints refer to those with an answer (0 - no pain, 1 - pain).

- Change in digital ulcer count from baseline to Week 24.

The digital ulcer count corresponds to the sum of active or new plus indeterminate/healing digital ulcers secondary to SSc (see [Appendix I](#)).

- CRISS.

The Composite Response Index for Diffuse Cutaneous Systemic Sclerosis (CRISS) tool summarizes the changes in the clinical and patient-reported outcomes using a single composite score that reflects the probability that the patient with dcSSc has improved.

CRISS is obtained in a 2-step process as described below.

Step 1: Patients who develop new or worsening of cardiopulmonary and/or renal involvement due to SSc are considered as not improved (irrespective of improvement in other core items) and assigned a probability of improving equal to 0.0. Specifically if a subject develops any of the following:

- New scleroderma renal crisis.
- Decline in FVC% predicted $\geq 15\%$ (relative), confirmed by another FVC% within a month, high resolution computer tomography (HRCT) to confirm ILD (if previous HRCT of chest did not show ILD) and FVC% predicted below 80% predicted*.
- New onset of left ventricular failure (defined as left ventricular ejection fraction $\leq 45\%$) requiring treatment*.
- New onset of Pulmonary Arterial Hypertension (PAH) on right heart catheterization requiring treatment*. PAH is defined as mean pulmonary artery pressure ≥ 25 mm Hg at rest and an end-expiratory pulmonary artery wedge pressure ≤ 15 mm Hg and a pulmonary vascular resistance > 3 Wood units.

*Attributable to SSc

Step 2: For the remaining patients, Step 2 involves computing the predicted probability of improving for each subject using the following equation (equation to derive predicted probabilities from a logistic regression model):

$$\frac{\exp(-5.54-0.81*\Delta\text{MRSS}+0.21*\Delta\text{FVC\%}-0.40*\Delta\text{Pt-glob}-0.44*\Delta\text{MD-glob}-3.41*\Delta\text{HAQ-DI})}{1+\exp(-5.54-0.81*\Delta\text{MRSS}+0.21*\Delta\text{FVC\%}-0.40*\Delta\text{Pt-glob}-0.44*\Delta\text{MD-glob}-3.41*\Delta\text{HAQ-DI})}$$

ΔmRSS indicates the change in mRSS from baseline, $\Delta\text{FVC\%}$ denotes the change in FVC% predicted from baseline, $\Delta\text{Pt-glob}$ indicates the change in patient global assessment (as per Likert scale), $\Delta\text{MD-glob}$ denotes the change in physician global assessment (as per Likert scale) (see [Appendix G](#)), and $\Delta\text{HAQ-DI}$ is the change in HAQ-DI. All changes are absolute change ($\text{Time}_2 - \text{Time}_{\text{baseline}}$).

- Change in EQ-5D-5L index from baseline to Week 24.

EQ-5D-5L (see [Appendix F](#)) is a generic measure of health status developed by the EuroQol Group in order to provide a simple measure of health for clinical and economic appraisal. It measures 5 dimensions: mobility, self-care, usual activities, pain/discomfort and anxiety/depression. Each of the dimensions is divided into 5 levels of perceived problems ranging from 1 (no problem) to 5 (extreme problem).

For each patient, a 5-digit score is obtained by combining each of the 5 dimensions. For example, score 11111 indicates no problems on any of the 5 dimensions, while score 12345 indicates no problems with mobility, slight problems with washing or dressing, moderate problems with doing usual activities, severe pain or discomfort and extreme anxiety or depression. For each patient, the EQ-5D-5L index, ranging from -0.594 to 1.0 is derived from this score using the United Kingdom population-based scoring ([4](#), [5](#)).

In addition, the EQ-5D has a single VAS to evaluate perceived current health. The VAS is scored between 0 and 100 by using the values indicated on the VAS where the patient has placed their mark, or by using the value written by the patient.

For index and VAS, missing data will not be imputed. Ambiguous values (eg, 2 boxes are ticked for a single dimension) on the health state/index score are treated as missing.

- Change in efficacy endpoints (mRSS, HAQ-DI, VAS from SHAQ, observed FVC, % predicted FVC, observed DLco [corrected for hemoglobin], % predicted DLco [corrected for hemoglobin], UCLA SCTC GIT 2.0 score, TJC28, digital ulcer count, CRISS, and EQ-5D-5L index and VAS) from baseline to Week 35 (up to end of follow-up period) and proportion of patients with improvement in mRSS of at least 20%, 40% and 60% from baseline to Week 35.

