9.1.4.3 Gastrointestinal Manifestations

The UCLA SCTC GIT 2.0 instrument is a validated self-reported questionnaire used to assess QOL related to gastrointestinal function in patients with SSc (15). It employs a 7-multi-item scale with areas of reflux, distention/bloating, diarrhea, fecal soiling, constipation, emotional well-being, and social functioning. This will be captured at all visits except V1 and V3.

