2.4.4.4 Analyses of exploratory efficacy endpoints

All exploratory endpoints are described in [Section 2.1.4](#) and will be analyzed using the ITT population unless otherwise specified.

Change in continuous exploratory efficacy endpoints from baseline to Week 24 will be analyzed using the same MMRM model as for the primary and continuous secondary efficacy endpoints. Specifically, the model will contain fixed categorical effects of treatment group, randomization strata (as per IRT), time point, randomization strata-by-time point interaction and treatment-by-time point interaction, as well as the continuous fixed covariates of corresponding baseline value and baseline-by-time point interaction. All post-baseline data available from Week 4 to Week 24 analysis windows will be included in the analysis, regardless of adherence to treatment. Missing data will be accounted for by the MMRM. This model will provide baseline adjusted LSmeans estimated at Week 24 in both treatment groups with their corresponding 95% CIs. The SAR156597 to placebo differences of these estimates will be provided with its corresponding 95% and 90% CIs and p-value.

Change in continuous exploratory efficacy endpoints from baseline to Week 35 will be analyzed using the same model. All post-baseline data available from Week 4 to Week 35 analysis windows will be included in the analysis, regardless of adherence to treatment.

2.4.4.4.1 mRSS

Responder rates (proportion of patients with an improvement from baseline in mRSS of at least 20%, 40% and 60%) at Week 24 and Week 35 will be analyzed using a logistic regression with the categorical effects of treatment group and randomization strata (as per IRT) and the continuous effect of mRSS at baseline. This model will provide the SAR156597 to placebo odds ratio estimate and its 95% and 90% confidence intervals. The p-value will be obtained from the

Wald Chi-square test. Patients with missing value at Week 24, respectively Week 35, will be considered as non-responders. Cumulative distribution function (CDF) graphs will be also presented (percentage of patients according to the relative improvement from baseline in mRSS) at W24 and W35.

Furthermore, the change from baseline to Week 35 will be analyzed using the MMRM model described in [Section 2.4.4.4](#).

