2.4.4.4.3 UCLA SCTC GIT 2.0 score

Change in UCLA SCTC GIT 2.0 score from baseline to Week 24 and from baseline to Week 35 will be analyzed using the MMRM model described in [Section 2.4.4.4](#).

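### Read literally, SAP 2.1.4 lets one blank constipation item void a UCLA SCTC GIT 2.0 total that does not use the constipation scale

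*SAP*

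**What the plan says.** SAP 2.1.4 describes the instrument: "The UCLA SCTC GIT 2.0 Questionnaire includes 34 items and 7 multi-item scales". Constipation is one of the seven scales. On the total score it says that "it is calculated as the average of all scales (except constipation) and ranges from 0.00 to 2.83". The missing-data rule follows at once: "If one item is missing, the UCLA SCTC GIT 2.0 score will be considered missing". No item or scale is exempted.

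Nothing elsewhere relaxes this. Protocol 9.1.4.3 gives the collection schedule ("This will be captured at all visits except V1 and V3") but no scoring rule. SAP 2.4.4.4.3 sends the change from baseline to the MMRM of SAP 2.4.4.4, which carries the baseline value as a covariate and states: "Missing data will be accounted for by the MMRM". The imputation steps in SAP 2.5.2 cover FVC, DLco and CRISS only.

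**The concern.** A missing-item rule should protect a score from being computed on too little information. A constipation item carries no information for this total, so voiding the total when one is blank protects nothing and throws away a valid value.

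The rule is also strict for the contributing items, since one blank on a 34-item self-completed form discards all the other answers. The MMRM can borrow from the patient's other visits, but it cannot use answers that the derivation has already dropped.

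What is at stake is the gastrointestinal part of the exploratory objective. The only other patient-reported gastrointestinal efficacy measure is the single SHAQ VAS.

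**Working it through.** **Inputs.** From SAP 2.1.4: 34 items; 7 scales, of which 6 enter the total; scale maxima of 2.00 for diarrhea, 2.50 for constipation and 3.00 for the other five. From SAP 1.4: 94 patients. From the Protocol flow chart: forms at V2, V4, V5, V6, V7 and V8, so one pre-dose form. Assumed, because the documents do not give them: the missing rate per item, p; and the number of constipation items, taken as 4 (the questionnaire in SAP Appendix E is not shown).

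**Step 1: reproduce the stated range.** Without constipation the maximum is (5 × 3.00 + 2.00)/6 = 17/6 = 2.83, which is the SAP's figure. With constipation it would be (17 + 2.50)/7 = 19.5/7 = 2.79, which does not match. Constipation is therefore outside the total.

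**Step 2: consequence by visit.** A void form after baseline loses that visit, and the patient's other visits stay in the MMRM. A void form at V2 leaves no baseline, hence no change score at any visit and no covariate value, so the patient drops out of this analysis.

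**Step 3: size of the whole rule, independent blanks.** The share of forms voided is 1 − (1 − p)^34. If only the assumed 30 contributing items counted, it would be 1 − (1 − p)^30. The part due to constipation items alone is the difference, (1 − p)^30 × [1 − (1 − p)^4].

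| p per item | voided, 34 items | of 94 forms | voided, 30 items | constipation alone (points) |
|---|---|---|---|---|
| 0.1% | 3.3% | 3.1 | 3.0% | 0.4 |
| 0.5% | 15.7% | 14.7 | 14.0% | 1.7 |
| 1% | 28.9% | 27.2 | 26.0% | 2.9 |
| 2% | 49.7% | 46.7 | 45.5% | 4.2 |

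The last column uses unrounded values (for p = 0.1%: 3.34 − 2.96 = 0.39). With 2 to 8 constipation items instead of 4, the figure at p = 1% runs from 1.4 to 5.9 points.

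**Step 4: clustered blanks.** If some patients skip items more than others, the same average rate spoils fewer forms. In a beta-binomial model with mean p and intraclass correlation ρ, set a = p(1 − ρ)/ρ and b = (1 − p)(1 − ρ)/ρ. The chance of a complete form is then Γ(b + 34)Γ(a + b)/[Γ(b)Γ(a + b + 34)]. At p = 1% the share voided is 18.0% for ρ = 0.05, 13.5% for ρ = 0.1 and 6.7% for ρ = 0.3, against 28.9% under independence.

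**Step 5: what a within-scale tolerance would do.** For illustration, take six scales of five items, with a scale scored when at least half its items are answered (void at three or more blanks), and all six scales required. At p = 2% with independent blanks, 0.05% of forms are lost. The five-item layout is an assumption.

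**The case against.** The missing-item sentence comes straight after the definition of the total. It could be meant to cover only the items that feed that total. That reading is possible, but the text does not say so, and a programmer following it literally would check all 34 items. This supports a clarification rather than the view that nothing needs changing.

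A reader might infer that the rule is out of line with the rest of the SAP. It is stricter than the HAQ-DI rule ("The patient must have a score for at least 6 of the 8 domains for the composite score to be calculated") and the TJC28 rule, which fills in missing joints from the scored ones. But the mRSS, the primary endpoint, is also missing if any of its 17 areas is missing (SAP 2.1.3.1). The EQ-5D-5L index and the SHAQ VAS scores are not imputed either. The SAP mixes tolerant and complete-item rules, so strictness alone is no inconsistency. The constipation point does not depend on that comparison: all 17 mRSS areas enter the mRSS, whereas constipation items do not enter the GIT total.

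Conduct should also keep blanks down. Protocol 10.1 has patients complete questionnaires at the site, and Protocol 13.4 provides for data queries. Neither guarantees complete forms, but both argue against assuming a high rate.

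Finally, the endpoint is exploratory and its p-values are descriptive (SAP 2.4.4.3), so no confirmatory conclusion turns on it. That stands in full.

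**Conclusion.** The point holds as a minor defect of wording with a free remedy. On a literal reading, a blank constipation item voids a total that excludes constipation, and at Visit 2 that removes the patient from the GIT analysis. This follows from the text and from the 2.83 maximum, whatever the rate of blanks.

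A reader might go further and infer that a large share of usable scores will be lost. The documents do not support that, because they give no item non-response rate. The loss from the whole one-item rule ranges from a few percent to more than a quarter of forms for rates of 0.1% to 1% under independence, and clustering lowers it. Nor should voided forms be read as patients lost at each visit, since only a void baseline form takes the patient out of the model.

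Nearly all of the possible loss comes from the one-item rule itself. The constipation items are the clearer error but the smaller part.

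**What to change.** Add one sentence to SAP 2.1.4: only items of the six scales that enter the total determine whether the total is missing, so constipation items do not count. It costs one line of derivation code. There is no downside, because every recovered total is computed from complete contributing scales.

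Optionally, before unblinding, add a supportive analysis that scores each contributing scale from its answered items under a prespecified minimum and still requires all six scales for the total. Keep the complete-item score for comparison. The cost is a second derivation and some averaging within scales for patients with a skipped item. The documents do not settle the minimum, so it has to be chosen and stated in advance.

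A rule that accepts five of the six scales should not be adopted, because it changes the range of the total. Without diarrhea the maximum becomes 15/5 = 3.00, and without any one of the others it becomes (4 × 3.00 + 2.00)/5 = 2.80, against 2.83 with all six. A change score could then compare totals of different composition.
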